At the beginning of the intervention, we will emphasize to caregivers that text message is only allowed for scheduling or making changes to scheduled intervention times, not for other purposes. In case caregivers would like other family members to attend the intervention with them, interventionists will inform caregivers in advance that the intervention includes components that ask caregivers about caregiving difficulties, private psychological issues, or family problems; thus, it is up to caregivers to decide whether to include family members into the calls. If they feel comfortable sharing when there are with other family members, they may choose so to let other family members attend the intervention. However, if caregivers are not comfortable, we will advise them to attend the intervention by themselves.

Quality control of the intervention

At the end of each session, interventionists will complete a standardized treatment form (i.e., Interventionist Delivery Assessment (IA)) that summarizes the session either on REDCap or hardcopy.

For training purposes only and quality control of the intervention, we will audio record a subsample of the intervention sessions. These audio recordings will be stored securely and will not be linked to participant’s name or other identifying information. These will not be used for research purposes. The recordings will be reviewed within 3 months and then destroyed. Participants may continue their

PROTOCOL TITLE: A Phone Intervention for Family Dementia Caregivers in Vietnam

participation in this study without consenting to these recordings and having any impact on their participation.

In general, a session will be conducted by one interventionist. However, in some cases, there will be another interventionist who will join the session as a supportive person to enhance the quality control of the intervention.

Supervision of all interventionists will take place during a weekly supervision meeting (in-person or by phone) with senior members of the research team.

Enhanced Control:

Caregivers in the enhanced control group will receive a single phone session in which they will receive education about ADRD including written materials.

Outcome assessments:

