from the key linking personal information (e.g., name, date of birth, address, phone number) and identifiers, 3) data will be kept on a secure server that is only accessible to research staff, 4) at the conclusion of the study, the key linking identifiers and personal information will be destroyed, 5) all research personnel in the U.S. who have access to the patient data will receive training on conducting human research (e.g., NIH online course) – all investigators and research staff in Vietnam will participate in the local equivalent of this training.

9) Data and/or Specimen Banking

All data will be stored on a secure server at in Vietnam. De-identified data will be transferred to UC Davis and the University of Minnesota (UMN) electronically through an encrypted zip file. After the study, the key linking personal identifiers to the survey data will be destroyed.

10) Provisions to Monitor the Data to Ensure the Safety of Subjects

Case review will occur on a weekly basis with a team that includes the interventionists, the PI and investigators from the NGH, UCD, and UMN. The caregiver's level of distress and any indicators of elder abuse/neglect will be reviewed at each session.

This study will have a Safety Officer (SO), who will meet 1-2 times each year to review the progress of the study, including adverse events, procedures for maintaining the confidentiality of data, and the quality of data collection, management, and analyses. The SO will also review any issues that arise in terms of conflict of interest or serious adverse events as needed. The SO will report directly to the funder (i.e., NIA).

[name] will be responsible for overall monitoring and appropriate reporting of adverse events including serious adverse events that occur during the study. Plans regarding reporting of adverse events will follow guidelines and policies of UC Davis as well as NIH.

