Adverse events will include events untoward or unfavorable mental or physical health-related occurrence in a human subject that is temporally associated with the subject's participation in the research, regardless of whether they are considered related to the subject's participation in the research. Examples of such events that might occur include incidents of brief hospitalization, caregiver distress or depression, instances of elder abuse or neglect, and other unanticipated events. Serious adverse events will be further defined as those events that seriously jeopardize the participant's health, including prolonged hospitalization, suicide attempts, and death. The overall goal of this plan is to have both serious adverse events (SAE) and non-serious adverse events (NSAE) that are viewed as likely (i.e., 50% or higher) related to study participation reported to both the UCD IRB and NIH in a timely fashion.

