As a routine part of training, intervention study staff will be educated to monitor for these events and to report them to the research staff. Interventionists or other research staff will complete AE Field Report Form and provide this to NGH RCT leads (i.e., [name] and [name]) within 48 hours. Upon receiving the report, [name] must confirm that she has received the report and is available to act upon it. [name] will review AE Field Report Form, complete AE Form and, if it is a SAE, complete SAE Form and send to study PIs ([name], [name], and [name]) within 48 hours. [name] will serve as back-up in case [name] is not available. Within 2 working days of receipt of the information about the SAE, [name] will share this information with the research team and the SO. If the SAE is viewed as likely (i.e., >50% probability) of being related to participation in the study, the SAE will be reported to the UCD IRB and to NIH within 2 working days of this determination with the goal of reporting all such events to UCD IRB and to the NIH PO within 5 working days of the time [name] became aware of the event. NSAE will be shared with the core members of the research team, including Drs. [name], [name] and [name], at their regular biweekly meetings. If NSAE are deemed as possibly related to study participation they will be reported to the SO within one week and, if the SO views them as “probably” (i.e., >50% likelihood) of being related to study participation, to the UCD IRB and NIH PO within 5 working days. All SAE and NSAE that are viewed as not likely to be related to research participation will be reported on an annual basis to the NIH PO as part of the progress report as well as to the IRBs.

11) Withdrawal of Subjects

Subjects (patients and family members) may withdraw at any time. If they withdraw from the study, they will be given the option of having their records destroyed.

12) Risks to Subjects

The main risks associated with this study: 1) discomfort or mild distress because of the intervention, 2) inconvenience because of the need to fill out the study questionnaires, and 3) loss of confidentiality. These risks are similar to the risk of undergoing routine assessments in healthcare clinics in Vietnam. Specific steps are being taken to address each category of risk (please see Section 16).

13) Potential Benefits to Subjects

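### Scheduled safety enquiry follows the number of sessions (5 to 9 against 1), so adverse-event counts by arm would partly reflect contact frequency

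*Protocol*

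**What the plan says.** Protocol section 10 sets out how events come to light. On scheduled review it says that caregiver distress and "any indicators of elder abuse/neglect will be reviewed at each session". On oversight: "Case review will occur on a weekly basis with a team that includes the interventionists". On training: "intervention study staff will be educated to monitor for these events and to report them to the research staff". On filing: "Interventionists or other research staff will complete AE Field Report Form".

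The same section defines an adverse event by its timing relative to participation, whether or not it is thought to be related, so events in control families are in scope. It gives these illustrations: "Examples of such events that might occur include incidents of brief hospitalization, caregiver distress or depression, instances of elder abuse or neglect".

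Protocol section 7 fixes the contacts. The intervention arm has a home enrolment visit (session 0), four to six core phone sessions and, optionally, one or two maintenance sessions. For the other arm: "Caregivers in the enhanced control group will receive a single phone session". A masked assessor telephones both arms at baseline and 3 months. The measures named for those calls are ZBI-6 and PHQ-4; no adverse-event question is mentioned.

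The SAP names burden and depressive/anxiety symptoms as outcomes. Its text describes no adverse-event analysis.

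**The concern.** Distress and abuse or neglect are the kinds of event that tend to surface only when someone asks. Here the asking is tied to sessions, and the number of sessions is set by the arm. The one later contact that is the same in both arms carries no stated event enquiry. Two things are at stake.

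- **Interpretation.** The Safety Officer reviews adverse events, and a trial report will normally say something about safety in each arm. An excess in the intervention arm could be harm or could be better detection, and a real benefit could be hidden in the same way. Section 12 lists distress caused by the intervention as the first main risk, and the control arm is the natural benchmark for it. Expedited reporting also turns on whether an event is judged more than 50% likely to be related, which is harder to judge without a comparable background rate.
- **Oversight.** Both arms are selected for burden (ZBI-4 of at least 6, section 4), and section 16 expects that abuse or neglect may be detected and need action. Control families have fewer scheduled occasions on which it could be noticed.

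**Working it through.** The plan states no figure on this point, so there is none to reproduce. The check counts contacts and then illustrates what unequal contact could do.

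**Step 1: contacts per caregiver (Protocol section 7).**
- Intervention, minimum: 1 + 4 = 5. Maximum: 1 + 6 + 2 = 9.
- Control: 1, crediting the single education call as a session at which the review takes place.
- With 30 caregivers per arm: 5 × 30 = 150 to 9 × 30 = 270 session contacts, against 30.
- If the 3-month call is also credited as an enquiry in both arms, which the protocol does not say: 6 to 10 against 2.

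The contact ratio is therefore 5:1 to 9:1 on sessions alone, or 3:1 to 5:1 with the 3-month call credited.

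**Step 2: illustration of unequal detection.** Let q be the probability that one contact brings an existing event to light, and k the number of contacts. Then

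P(detected) = 1 − (1 − q)^k.

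With the same true risk in both arms, the apparent ratio of events is [1 − (1 − q)^k_int] / [1 − (1 − q)^k_con]. The documents give no value for q; 0.1 to 0.5 is assumed.

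| q | Sessions only: detected, intervention (k = 5 to 9) vs control (k = 1) | Ratio | 3-month call credited: detected, intervention (k = 6 to 10) vs control (k = 2) | Ratio |
|---|---|---|---|---|
| 0.1 | 0.41 to 0.61 vs 0.10 | 4.1 to 6.1 | 0.47 to 0.65 vs 0.19 | 2.5 to 3.4 |
| 0.3 | 0.83 to 0.96 vs 0.30 | 2.8 to 3.2 | 0.88 to 0.97 vs 0.51 | 1.7 to 1.9 |
| 0.5 | 0.97 to 1.00 vs 0.50 | 1.9 to 2.0 | 0.98 to 1.00 vs 0.75 | 1.3 |

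Worked example at q = 0.1 on sessions alone: 1 − 0.9^5 = 0.41 and 1 − 0.9^9 = 0.61, against 0.10.

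**Step 3: in events.** Assume a true risk of 20% in both arms, so 0.20 × 30 = 6 true events per arm. On sessions alone, the expected numbers detected are 2.5 to 3.7 against 0.6 at q = 0.1, 5.0 to 5.8 against 1.8 at q = 0.3, and 5.8 to 6.0 against 3.0 at q = 0.5.

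**Step 4: with equal enquiry.** If k is the same in both arms, the ratio is 1.0 for every q.

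**Limits of the model.** It treats each event as present before the first contact and as equally and independently detectable at every contact. Real events arise over three months. The timing of the control session is not stated; if it comes early, later control events have no scheduled detection point. The direction is firm; the multiple is not.

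**The case against.** The strongest reply is that the documents plan no comparison that this would spoil. The SAP contains no event test or table by arm. Section 10 handles events case by case on relatedness, and it does not say that the Safety Officer receives tallies by arm. The study is declared minimal risk, and placing most monitoring where the research exposure lies is a defensible choice in a pilot. All of this stands, and it limits the reach of the point.

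A reader might go further in three ways that the text does not support.

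- **That controls are unmonitored.** Review at each session is not expressly confined to the intervention arm, so the control session may count, and the working credits it. Research staff other than interventionists may file an event form. PHQ-4 is collected identically in both arms, so mood can be compared as an outcome, although the scale is not an adverse-event enquiry and does not cover hospitalisation, abuse or death. The training sentence might even be read as covering everyone working on the study, although it separates those trained from the research staff to whom they report. On that wider reading the training gap closes, but the lack of a scheduled enquiry in controls after their one session remains.
- **That a several-fold spurious excess is to be expected.** The multiple rests on an assumed q and falls to 1.3 at q = 0.5 with the 3-month call credited. Deaths and long hospitalisations depend less on contact frequency, so no single ratio fits all event types.
- **That the efficacy results are biased.** Burden and depressive/anxiety symptoms are measured on the same schedule in both arms by a masked assessor.

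Section 10 also defers to institutional and NIH reporting policies that are not reproduced. They may add requirements, but nothing in the protocol schedules an enquiry that is equal across arms.

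**Conclusion.** The point holds as one about ascertainment. Followed as written, the plan offers 5 to 9 scheduled occasions for finding contact-dependent events in an intervention caregiver and one in a control caregiver, with no stated event enquiry on the later call that both arms share. Event counts by arm would partly measure contact. The size is illustrative: about 1.3 to 6 times more recorded events in the intervention arm at equal true risk, for q between 0.1 and 0.5, with or without credit for the 3-month call. The effect is greatest for distress and for abuse or neglect.

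The primary and secondary analyses are untouched. The consequence is for any safety statement by arm, for the Safety Officer's reading of the events and for oversight of control families. The change is worth making, but the trial's main result does not depend on it.

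**What to change.** At the 3-month call in both arms, once ZBI-6 and PHQ-4 are recorded, have the assessor ask one fixed list of the protocol's own event types over the preceding three months: hospitalisation, distress or depression, abuse or neglect, suicide attempt, death, and any other event. The assessor then files the AE Field Report Form. Give the assessor the same adverse-event training as the interventionists. State in the SAP that any between-arm event count uses these answers only, and that events found during sessions are listed separately with how they were found.

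The cost is a sentence in the protocol, one in the SAP, some training, and a few minutes on each of 60 calls already planned. There is a small risk of unblinding, which falls after the outcomes for that caregiver are recorded. The change gives both arms one equal enquiry. It does not make detection of control-arm events any earlier, and the protocol should not present it as doing so.

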### *Statistical Analysis Plan*

RCT outcomes include caregiver burden (primary) and depressive/anxiety symptoms (secondary). Preliminary analyses will compare the two groups at baseline on participant characteristics and primary outcomes using t-tests or chi-squared tests as appropriate; non-parametric versions will be used if needed. For each outcome, the primary assessment of efficacy will be based on intent-to-treat analyses. Difference scores on the outcomes between the two assessments will be computed. Within-group change will be assessed with a paired t-test or the Wilcoxon signed rank test, as appropriate, while between-group differences in change will be assessed with a two-sample t-test or the Wilcoxon rank sum test. If groups differ at baseline, analysis of covariance will be used with the 3-month assessment as the outcome and the baseline assessment as a covariate; group will be the primary predictor of interest and any additional participant characteristics found to be different at baseline will also be considered as covariates. Transformations or generalized linear models for non-normal data will be considered if model assumptions are violated. The data were imported into the REDcap database and analyzed using SAS statistical software. A p-value less than 0.05 is considered statistically significant.

Power analysis: With 30 participants per group, we will have 80% power to detect a difference as small as 0.64 standard deviations between the groups, assuming a one-sided test (as this is a pilot study) and alpha=0.05. If alpha is reduced to 0.025 to account for the two outcomes, the minimum detectable difference is 0.72 standard deviations. Our pilot RCT using the original REACH VN showed effect sizes of at least 0.9, so the current study is powered to detect smaller effects, which might be expected in a telehealth administration of the intervention.

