6) Study Endpoints

This is a time-limited intervention lasting up to 3 months with independent assessment of outcomes at baseline and 3 months.

7) Procedures Involved

Study design: A two arm, 3-month follow up, cluster randomized controlled trial of 60 caregivers (30 in REACH VN phone intervention group and 30 in enhanced control group) will be conducted.

Setting: Thach That District, a semi-rural area in Hanoi, Vietnam.

Recruitment:

PROTOCOL TITLE: A Phone Intervention for Family Dementia Caregivers in Vietnam

In collaboration with commune health stations, community-based screening will be conducted to identify “at risk” older adults with dementia and their family caregivers.

Staff from the National Geriatric Hospital (NGH) will train local staff (e.g., village health workers) to identify people at high risk for dementia from their caseloads, including those with a history of significant memory problems, behavioral issues and evidence of functional decline. Staff from local health clinics will contact potential participants by phone or in-person, provide information about the project, and invite them to participate in screening to determine their eligibility. Verbal consent will be obtained from an older adult and a family member prior to screening by research staff. Those who consent to participate in the screening will undergo an assessment including a brief neurological exam, cognitive testing and dementia stage using standardized instruments, including the Mini-Cog, NPI-Q, and CDR. The assessments will be conducted by physicians, neurologists, or healthcare professionals trained by NGH. Once an older adult has been determined to meet criteria for dementia (i.e., CDR ≥ 1), we will identify the adult family member who is providing the most day-to-day care and invite them to participate in a brief screening to determine their eligibility. If they are eligible, we will invite them to participate in the study and obtain verbal consent.

A screening log will be kept to document number and reasons of participants who do not meet the inclusion criteria, decline to participate, or any other reasons.

Consent:

Because of the minimal risk of both screening and behavioral intervention, verbal consent will be obtained for both. As part of the consent process, all caregivers will be informed that this is a voluntary study and that they can withdraw at any time.

Randomization:

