Communes will be the unit of randomization and randomization assignments will be generated using a block randomization function in R for each stratum with a 1:1 ratio for two groups: intervention (n= approximately 8 clusters or 30 caregivers) or enhanced usual care (n= approximately 8 clusters or 30 caregivers). The UC Davis Biostatistician will be responsible for generating randomization codes and assigning randomization codes to communes. The biostatistician will communicate cluster assignment to the principal investigator (PI) to convey to the study team in Vietnam of when communes have been randomized.

Clusters will need to be in Thach That District and have a minimum of 3 participants and a maximum of 15 participants.

Blinding:

A trained outcome assessor who conducts data collection will be blinded regarding group assignments.

REACH VN Phone Intervention:

PROTOCOL TITLE: A Phone Intervention for Family Dementia Caregivers in Vietnam

Family caregivers in the intervention will receive a manualized multicomponent intervention, including psychoeducation, stress reduction, and skill-building, that will consist of 4-6 “core” sessions with the option for 1-2 “maintenance” sessions based on caregiver needs and clinical judgment with a trained staff (e.g., nurse, social worker, or community health worker) who has been certified to deliver the intervention. Interventionists will follow the interventionist manual that includes scripts, detailed descriptions of the goals for each session, and standardized forms.

The enrollment session (session 0) will be conducted face-to-face. Interventionists with village health workers will come to caregivers’ home to provide a caregiver notebook with information about dementia and management of common problems, check phone issues and signals, and conduct the risk priority intake assessment. The intervention sessions will be conducted over the phone with either audio or video call over the course of 1-3 months. The sessions will occur every 1–2 weeks depending on the needs and availability of family caregivers. Each intervention session will last between 30 minutes to an hour. In case caregivers are not able to concentrate on the session after the first 20-30 minutes, interventionists can end the session and make appointment to call back within 2-4 days (or whenever it is possible) to complete the session.

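### Communes are randomised, but the SAP's between-group tests and power figures treat the 60 caregivers as independent, so p-values are too small if outcomes correlate within commune

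*SAP*

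**What the plan says.** Protocol section 7 (Procedures Involved, Study design) describes a "cluster randomized controlled trial of 60 caregivers (30 in REACH VN phone intervention group and 30 in enhanced control group) will be conducted". Under Randomization it states: "Communes will be the unit of randomization and randomization assignments will be generated using a block randomization function in R for each stratum". The entry for the active arm reads "intervention (n= approximately 8 clusters or 30 caregivers", and the control arm has the same numbers. Clusters must "have a minimum of 3 participants and a maximum of 15 participants".

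The SAP, Statistical Analysis Plan, works on caregivers throughout. The default comparison is that "between-group differences in change will be assessed with a two-sample t-test or the Wilcoxon rank sum test". If the groups differ at baseline, "analysis of covariance will be used with the 3-month assessment as the outcome and the baseline assessment as a covariate", with group as the predictor of interest. The remaining fallback is: "Transformations or generalized linear models for non-normal data will be considered if model assumptions are violated".

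The power paragraph says: "With 30 participants per group, we will have 80% power to detect a difference as small as 0.64 standard deviations between the groups", one-sided at alpha 0.05. It gives 0.72 SD if alpha is reduced to 0.025 for the two outcomes.

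Neither document, as available, mentions an ICC, a design effect, a random commune effect, generalised estimating equations, cluster-robust variance or a commune-level summary.

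**The concern.** A two-sample t-test, a rank-sum test, an ordinary ANCOVA and an ordinary generalised linear model all assume independent observations. When communes are allocated, that holds only if the commune ICC of the analysed quantity is zero. For the default test that quantity is the change score. For the ANCOVA it is the 3-month score adjusted for baseline. With a positive ICC the standard errors are too small, so p-values compared with 0.05 are too small and any intervals from these models are too narrow.

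A zero ICC is hard to take for granted here. Protocol section 7 has caregivers identified through commune health stations and local staff caseloads, and village health workers join the enrolment visit in the intervention arm. Such influences can act after baseline, where a change score does not remove them.

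Protocol section 2 states an efficacy hypothesis for caregiver burden, and the SAP sets a significance threshold and claims 80% power. Both the test and the power claim are therefore affected.

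**Working it through.** **Inputs from the documents.** 30 caregivers per arm; about 8 communes per arm; mean commune size m = 30/8 = 3.75; 80% power; one-sided alpha 0.05 or 0.025.

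**Assumed.** The ICC of the analysed score, over 0 to 0.20.

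**1. Reproduce the plan's figures.** Detectable difference = (z for alpha + z for power) × sqrt(2/n).
- Alpha 0.05: (1.645 + 0.842) × sqrt(2/30) = 0.642 SD.
- Alpha 0.025: (1.960 + 0.842) × sqrt(2/30) = 0.723 SD.

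These match the stated 0.64 and 0.72, so the design effect used was 1.

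**2. Allow for clustering.**
- Design effect: DE = 1 + (3.75 − 1) × ICC.
- True error of a nominal 5% test: two-sided 2 × [1 − Φ(1.96/√DE)]; one-sided 1 − Φ(1.645/√DE).
- Detectable difference from DE alone: (z for alpha + z for power) × sqrt(2 × DE/30).
- Detectable difference for a commune-level test: noncentral t with 16 − 2 = 14 df and noncentrality d × sqrt(15/DE).

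| ICC | DE | Effective N | Error, two-sided | Error, one-sided | Detectable SD, alpha 0.05: DE alone / 14 df | Detectable SD, alpha 0.025: DE alone / 14 df | Power at 0.64 SD (alpha 0.05, 14 df) |
|---|---|---|---|---|---|---|---|
| 0 | 1 | 60 | 5.0% | 5.0% | 0.642 / 0.675 | 0.723 / 0.778 | 76% |
| 0.01 | 1.0275 | 58.4 | 5.3% | 5.2% | 0.651 / 0.685 | 0.733 / 0.789 | 75% |
| 0.05 | 1.1375 | 52.7 | 6.6% | 6.1% | 0.685 / 0.720 | 0.771 / 0.830 | 71% |
| 0.10 | 1.275 | 47.1 | 8.3% | 7.3% | 0.725 / 0.763 | 0.817 / 0.879 | 67% |
| 0.20 | 1.55 | 38.7 | 11.5% | 9.3% | 0.799 / 0.841 | 0.901 / 0.969 | 60% |

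The ICC 0 row separates the two effects: moving to 14 df costs 0.675 − 0.642 = 0.033 SD before any correlation is assumed.

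**3. Allow for stable commune effects.** With an overall baseline-to-follow-up correlation of 0.5 (assumed), the change-score ICC is 2 × ICC × (1 − autocorrelation), where ICC is cross-sectional and the autocorrelation is that of the commune effect over time. The baseline-adjusted ICC is ICC × (1.25 − autocorrelation)/0.75. At autocorrelation 1 the first is zero and the second is not. Simulated two-sided error (8 communes of 3–4 caregivers per arm, 10,000 replicates per scenario):

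| Commune autocorrelation | Test | ICC 0.05 | ICC 0.10 | ICC 0.20 |
|---|---|---|---|---|
| 1 | Change-score t-test | 5.1% | 5.2% | 5.1% |
| 1 | ANCOVA | 5.5% | 6.3% | 7.1% |
| 0.8 | Change-score t-test | 6.0% | 6.5% | 7.3% |
| 0.8 | ANCOVA | 6.1% | 7.1% | 8.7% |
| 0.5 | Change-score t-test | 6.8% | 8.2% | 11.8% |
| 0.5 | ANCOVA | 6.8% | 8.1% | 11.5% |

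**4. Allow for uneven communes.** With seven communes of 3 and one of 9 per arm, the simulated error of the caregiver-level t-test is 5.3%, 7.5%, 9.5% and 13.9% at analysed-score ICC 0.01, 0.05, 0.10 and 0.20.

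**5. Check the alternatives.** In the scenarios of step 3, a t-test on commune means rejected in 4.8–5.3% of trials and a rank-sum test on commune means in 4.6–5.2%. A mixed model with stratum and Kenward-Roger df rejected in 3.7–5.1% (1,500 replicates per scenario, Monte Carlo standard error about 0.6 points).

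**The case against.** The best defence is that the default test uses change scores. If commune effects do not move between baseline and 3 months, they cancel and the test is sound. Sessions are delivered to individual caregivers by phone, communes average under four participants, and this is a pilot whose aims include feasibility and acceptability. The documents give no ICC, so every magnitude above is conditional, and error near 11.5% needs an ICC of 0.20 in the analysed score itself. The only sidedness in the documents is one-sided, for which the inflation is smaller.

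All of this is fair about size. It does not restore the independence assumption. Full stability is not argued anywhere in the documents, and the ANCOVA is inflated even under it. The generalised linear model clause does not help either: it is optional, aimed at non-normality and names no cluster term. Pilot status lowers the stakes but does not remove the efficacy hypothesis or the power claim.

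Three caveats stand. Part of the rise in detectable difference comes from the 14 df rather than from correlation. One part of the SAP document was not available for this review, although the analysis section reads as complete. The SAP also describes the analysis in the past tense, so a change may now have to be a disclosed re-analysis.

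**Conclusion.** The concern holds. The planned analysis and the stated power ignore the unit of randomisation, and this should be corrected before the between-group p-values are relied on.

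The direction is certain if the ICC of the analysed score is positive; the size is not known. At ICC 0.01 the effect on error is negligible. At 0.05 to 0.10 a nominal two-sided 5% test runs at about 6.6% to 8.3%, and 80% power at 0.64 SD falls to about 71% to 67% on 14 df. Uneven commune sizes make the error worse.

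The SAP's reassurance that earlier effects were at least 0.9 SD also weakens. At alpha 0.025 the detectable difference on 14 df is 0.88 SD at ICC 0.10 and 0.97 SD at ICC 0.20.

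These figures rest on the assumed ICC range, on 16 communes of 3.75 caregivers on average and, for the simulations, on a baseline-to-follow-up correlation of 0.5 and two strata with no stratum effect.

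**What to change.** For both ZBI-6 and PHQ-4, name one primary between-group analysis that respects commune randomisation:

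- **Preferred:** a linear mixed model for the 3-month score, with arm, baseline score and randomisation stratum as fixed effects, a random intercept for commune and Kenward-Roger degrees of freedom.
- **Simpler alternative:** a t-test, or a rank-sum test if non-normal, on the roughly 16 commune means of baseline-adjusted residuals. This has at most 14 df, or 13 if two strata are fitted.

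The two are different analyses, so the choice must be fixed in advance. If the data have already been analysed, re-run the comparison and disclose the change. The strata are not defined in the documents and need to be.

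Label the within-group paired tests, which are also at caregiver level, as descriptive. Report the commune ICC with its confidence interval. Restate the detectable difference over a stated ICC range, including the ICC 0 line on 14 df.

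The cost is SAP wording and a few lines of SAS, provided the commune identifier is kept in the dataset. Standard errors will generally widen, and the two-sided 5% critical value rises from 2.00 (58 df) to 2.14 (14 df) for the commune-level test. The ICC will be imprecise: the commune variance was estimated as zero in 11–49% of simulated trials. In those trials the mixed model is close to the caregiver-level analysis, a weakness that the commune-mean test does not share.
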